10.4. Appendix 4: Contraceptive Guidance and Collection of Pregnancy Information

10.4.1. Definitions:

Woman of Childbearing Potential (WOCBP)

A woman is considered fertile following menarche and until becoming post-menopausal unless permanently sterile (see below).

If fertility is unclear (e.g., amenorrhea in adolescents or athletes) and a menstrual cycle cannot be confirmed before first dose of study intervention, additional evaluation should be considered.

Women in the following categories are not considered WOCBP

- Premenarchal
- Premenopausal female with 1 of the following:
 - Documented hysterectomy
 - Documented bilateral salpingectomy
 - Documented bilateral oophorectomy

For individuals with permanent infertility due to an alternate medical cause other than the above, (e.g., Mullerian agenesis, androgen insensitivity), investigator discretion should be applied to determining study entry.

Note: Documentation can come from the site personnel's: review of the participant's medical records, medical examination, or medical history interview.

- Postmenopausal female
 - A postmenopausal state is defined as no menses for 12 months without an alternative medical cause.
 - A high follicle stimulating hormone (FSH) level in the postmenopausal range may be used to confirm a postmenopausal state in women not using hormonal contraception or hormonal replacement therapy (HRT). However, in the absence of 12 months of amenorrhea, confirmation with more than one FSH measurement is required.
 - Females on HRT and whose menopausal status is in doubt will be required to use one of the non-estrogen hormonal highly effective contraception methods if they wish to continue their HRT during the study. Otherwise, they must discontinue HRT to allow confirmation of postmenopausal status before study enrollment.

10.4.2. Contraception Guidance:

CONTRACEPTIVES^a ALLOWED DURING THE STUDY INCLUDE:

- Highly Effective Methods^b That Have Low User Dependency Failure rate of <1% per year when used consistently and correctly.
 - Implantable progestogen-only hormone contraception associated with inhibition of ovulation^b
 - Intrauterine device (IUD)
 - Intrauterine hormone-releasing system (IUS) b
 - Bilateral tubal occlusion
 - Vasectomized partner

Note: Vasectomized partner is a highly effective contraceptive method provided that the partner is the sole sexual partner of the woman of childbearing potential and the absence of sperm has been confirmed. If not, an additional highly effective method of contraception should be used. Spermatogenesis cycle is approximately 90 days.

- Highly Effective Methods^b That Are User Dependent Failure rate of <1% per year when used consistently and correctly.
- Combined (estrogen- and progestogen-containing) hormonal contraception associated with inhibition of ovulation^c
- oral
- intravaginal
- transdermal
- injectable
- Progestogen-only hormone contraception associated with inhibition of ovulation^c
- oral
- injectable
- Sexual abstinence
- Note: Sexual abstinence is considered a highly effective method only if defined as
 refraining from heterosexual intercourse during the entire period of risk associated with
 the study intervention. The reliability of sexual abstinence needs to be evaluated in
 relation to the duration of the study and the preferred and usual lifestyle of the
 participant.

ACCEPTABLE METHODS^d

- Progestogen-only oral hormonal contraception where inhibition of ovulation is not the primary mode of action
- Male or female condom with or without spermicide^e
- Cervical cap, diaphragm, or sponge with spermicide
- A combination of male condom with either cervical cap, diaphragm, or sponge with

spermicide (double-barrier methods)c

- a. Contraceptive use by men or women should be consistent with local regulations regarding the use of contraceptive methods for those participating in clinical studies.
- b. Failure rate of <1% per year when used consistently and correctly. Typical use failure rates differ from those when used consistently and correctly.
- c. If locally required, in accordance with Clinical Trial Facilitation Group (CTFG) guidelines, acceptable contraceptive methods are limited to those which inhibit ovulation as the primary mode of action.
- d. Considered effective, but not highly effective failure rate of ≥1% per year. Periodic abstinence (calendar, sympto-thermal, post-ovulation methods), withdrawal (coitus interruptus), spermicides only, and lactational amenorrhoea method (LAM) are not acceptable methods of contraception.
- Male condom and female condom should not be used together (due to risk of failure with friction).

10.4.3. Collection of Pregnancy Information:

Female Participants who become pregnant

- Investigator will collect pregnancy information on any female participant, who becomes pregnant while participating in this study.
- The initial information will be recorded on the appropriate form and submitted to GSK within 24 hours of learning of a participant's pregnancy.
- Participant will be followed to determine the outcome of the pregnancy. The investigator will collect follow up information on participant and neonate, which will be forwarded to GSK Generally, follow-up will not be required for longer than 6 to 8 weeks beyond the estimated delivery date.
- Any termination of pregnancy will be reported, regardless of fetal status (presence or absence of anomalies) or indication for procedure.
- While pregnancy itself is not considered to be an AE or SAE, any pregnancy complication or elective termination of a pregnancy for medical reasons will be reported as an AE or SAE.
- A spontaneous abortion (occurring at <22 weeks gestational age) or still birth (occurring at >22 weeks gestational age) is always considered to be an SAE and will be reported as such.
- Any SAE occurring as a result of a post-study pregnancy which is considered reasonably related to the study intervention by the investigator, will be reported to GSK as described in Appendix 3. While the investigator is not obligated to actively seek this information in former study participants, he or she may learn of an SAE through spontaneous reporting.

Any female participant who becomes pregnant while participating

• will discontinue study intervention or be withdrawn from the study

10.5. Appendix 5: Genetics

USE/ANALYSIS OF DNA

- Genetic variation may impact a participant's response to study intervention, susceptibility, severity and progression of disease. Variable response to study intervention may be due to genetic determinants that impact drug absorption, distribution, metabolism, and excretion; mechanism of action of the drug; disease etiology; and/or molecular subtype of the disease being treated. Therefore, where local regulations and IRB/IEC allow, a blood sample will be collected for DNA analysis
- DNA samples will be used for research related to GSK3228836 or CHB and related diseases. They may also be used to develop tests/assays including diagnostic tests related to GSK3228836 or other 2'-MOE ASOs, and CHB. Genetic research may consist of the analysis of one or more candidate genes or the analysis of genetic markers throughout the genome or analysis of the entire genome (as appropriate)
- Additional analyses of DNA samples may be conducted if it is hypothesized that this may help further understand the clinical data.
- The samples may be analyzed as part of a multi-study assessment of genetic factors involved in the response to GSK3228836 or study interventions of this class. The results of genetic analyses may be reported in the clinical study report or in a separate study summary.
- The sponsor will store the DNA samples in a secure storage space with adequate measures to protect confidentiality.
- The samples will be retained while research on GSK3228836 (or study interventions of this class) or CHB continues but no longer than 15 years after the last participant last visit or other period as per local requirements.

10.6. Appendix 6: Liver Safety: Required Actions and Follow-up Assessments and Study Intervention Restart/Rechallenge Guidelines

Phase 2 liver chemistry stopping and increased monitoring criteria have been designed to assure participant safety and evaluate liver event etiology.

The procedures listed below are to be followed if a participant meets any of the liver chemistry stopping criteria defined in Section 7.1.1.

- Immediately withdraw the participant from study treatment.
- Notify the Medical Monitor within 24 hours of learning of the abnormality to confirm the participant's study treatment cessation and follow-up.
- Complete the Liver Event CRF.
- Complete the "Safety Follow-up Procedures" listed below.

Safety Follow-up Procedures for Participants Who Meet *Any* of The Stopping Criteria:

Viral hepatitis serology including:

- o Hepatitis A IgM antibody;
- Cytomegalovirus IgM antibody;
- Epstein-Barr viral capsid antigen IgM antibody (or if unavailable, obtain heterophile antibody or monospot testing);
- o Hepatitis E IgM antibody.
- o Hepatitis C virus RNA load
- o Hepatitis D virus antibody
- Obtain a blood sample for pharmacokinetic (PK) analysis as soon as possible following the occurrence of an event. Record the date/time of the PK blood sample collection and the date/time of the last dose of study treatment prior to blood sample collection on the CRF. If the date or time of the last dose is unclear, provide the participant's best approximation. Instructions for sample handling and shipping are included in the Study Reference Manual (SRM).
 - Serum creatine phosphokinase (CPK) and lactate dehydrogenase (LDH).
 - Fractionate bilirubin, if total bilirubin ≥ 1.5 X upper limit of normal (ULN)
 - Assess eosinophilia
 - Record the appearance or worsening of clinical symptoms of hepatitis (fatigue, nausea, vomiting, right upper quadrant pain or tenderness, fever, rash or eosinophilia) as relevant on the Adverse Event (AE) CRF.

- Record use of concomitant medications, acetaminophen, herbal remedies, other over the counter medications, or putative hepatotoxins on the Concomitant Medications CRF.
- Record alcohol use on the Liver Events CRF.

The following are required for participants who meet the ALT and bilirubin stopping criteria but are optional for other abnormal liver chemistries.

- Anti-nuclear antibody, anti-smooth muscle antibody, Type 1 anti-liver kidney microsomal antibodies and quantitative total immunoglobulin G (IgG or gamma globulins).
- Serum acetaminophen adduct high performance liquid chromatography (HPLC) assay (quantifies potential acetaminophen contribution to liver injury in participants with definite or likely acetaminophen use in the preceding week [James, 2009]), if available.
- Liver imaging (ultrasound, magnetic resonance, or computerized tomography) or Liver biopsy to evaluate liver disease.
- The Liver Imaging and/or Liver Biopsy CRFs are also to be completed if these tests are performed.

Restart Following Transient Resolving Liver Stopping Events Not Related to Study Intervention

Restart refers to resuming study intervention following liver stopping events in which there is a clear underlying cause (other than drug-induced liver injury [DILI]) of the liver event (e.g. biliary obstruction, pancreatic events, hypotension, acute viral hepatitis). Furthermore, restart is not permitted following liver stopping event when the underlying cause was alcohol-related hepatitis.

- Approval by GSK for study intervention restart can be considered where:
 - Investigator requests consideration for study intervention restart if liver chemistries have a clear underlying cause (e.g., biliary obstruction, hypotension and liver chemistries have improved to normal or are within 1.5 x baseline and ALT <3xULN).
 - Possible study intervention-induced liver injury has been excluded by the investigator and the study team. This includes the absence of markers of hypersensitivity (otherwise unexplained fever, rash, eosinophilia). Where a study intervention has a confirmed genetic marker associated with liver injury, the presence of the marker should be excluded. If study intervention-related liver injury cannot be excluded, the guidance on rechallenge will apply.
- There is no evidence of alcohol-related hepatitis.
- Institutional Review Boards (IRB)/Independent Ethics Committees (IEC) approval of study intervention restart (as required) has been obtained.

If restart of study intervention is approved by GSK Medical Governance in writing:

- The participant must be provided with a clear description of the possible benefits and risks of study intervention administration including the possibility of recurrent, more severe liver injury or death.
- The participant must also provide signed informed consent specifically for the restart of study intervention. Documentation of informed consent must be recorded in the study file.
- Study intervention must be administered at the dose specified by GSK
- Participants approved by GSK for restart of study intervention must return to the clinic twice a week for liver function tests until stable liver function tests have been demonstrated and then standard laboratory monitoring may resume as per protocol.
- If the participant meets protocol-defined liver chemistry stopping criteria after study intervention restart, study intervention should be permanently discontinued.
- The Medical Monitor, and the IRB/IEC, must be informed of the outcome for the participant following study intervention restart.
- GSK must be notified of any adverse events.

10.7. Appendix 7: Country-specific requirements

10.7.1. China

The following sections outline China-specific changes from the main protocol.

In China, collection of exploratory/biomarker labs will be contingent on agreements with China regulatory (HGRAC), otherwise the SoA should be the same as the main study protocol.

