ALT ≥12x ULN and Bilirubin≤1.5x ULN and INR ≤1.5 (if available) ALT ≥3x ULN and	Hold dose Monitor twice weekly Additional lab assessments if not already done Take off hold: 150 mg SC weekly when ALT <10x ULN; increasing dose to 300 mg (if applicable) should be agreed with Medical Monitor Hold dose Monitor twice weekly Additional lab assessments if not	Permanently discontinue IMP if any of the following apply: ■ ALT ≥10x ULN >4 weeks ■ ALT ≥12x ULN recurs after IMP taken off hold Permanently discontinue IMP if the following recurs
1.5x ULN <bilirubin (="" uln="" ≤2x="">35% direct) and INR ≤1.5 (if available)</bilirubin>	already done Take off hold: 150 mg SC weekly when bilirubin returns to <1.5x ULN; increasing dose to 300 mg (if applicable) should be agreed with Medical Monitor For participants not receiving NA therapy at baseline, initiate NA therapy¹	after IMP taken off hold: 1.5x ULN <bilirubin (="" uln="" ≤2x="">35% direct) And INR ≤1.5 (if available)</bilirubin>
ALT ≥3x ULN and any of the following apply: • bilirubin >2x ULN (>35% direct) • associated with the appearance or worsening of hepatitis symptoms • INR >1.5 (if available)		Permanently discontinue IMP Monitor twice weekly until stable ALT Additional lab assessments if not already done For participants not receiving NA therapy at

ALT Level	Monitoring Plan	Discontinuation
		baseline, initiate NA therapy¹

ALT = alanine aminotransferase; IMP = investigational medicinal product; ULN = upper limit of normal 1. NA therapy may be subsequently discontinued if other tests (e.g., HBV DNA, HBsAg) rule out hepatitis B flare.

*Notes:

- Any abnormal laboratory parameters that meet the criteria for individual treatment discontinuation must be confirmed by retest of a new collection of blood samples as soon as possible.
- Deterioration considered clinically significant from the baseline in the liver parameters must be confirmed by retesting ALT, total bilirubin, direct bilirubin, and INR (if available).
- If one criterion in the list above is met and confirmed by retesting, further treatment may be discontinued for this participant after discussion with the Medical Monitor. Results of retesting must be evaluated before the next dose is administered.
- Monitor participant until liver chemistry abnormalities resolve, stabilize, or return to within baseline values.

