- 2. Urine testing will be standard for the protocol unless serum testing is required by local regulation or IRB/IEC or if urine testing is unavailable
- 3. Details of liver chemistry stopping criteria and required actions and follow-up assessments after liver stopping or monitoring event are given in Section 7.1 and Appendix 7. All events of ALT ≥3 × upper limit of normal (ULN) and bilirubin >2 × ULN (>35% direct bilirubin) or ALT ≥3 × ULN and international normalized ratio (INR) >1.5, if INR measured, which may indicate severe liver injury (possible Hy's Law), must be reported as an SAE (excluding studies of hepatic impairment or cirrhosis).

10.3. Appendix 3: Adverse Events: Definitions and Procedures for Recording, Evaluating, Follow-up, and Reporting

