	W9	W10	W11	W12	W13	W14	W15	W16	W17	W18	W19	W20	W21	W22	W23	W24
HBV RNA, HBcrAg and Sequencing (HBV Genotype/phenotype; HBV DNA and/or RNA)				Х				Х				Х				Х
Complement C3, Complement C4, hs- CRP, MCP-1	Х		Х		Х		Х		Х		Х		х		X	
Complement C5a, Complement factor Bb	Х		Х		Х		Х		Х		Х		Х		Х	
ANCA, Ang II	Χ				Χ				Χ				Χ			
PK ³	Χ	Χ	Χ	Χ	Χ	Χ	Χ	Χ	Χ	Χ	Χ	Χ	Χ	Χ	Χ	Χ
PBMC Collection for immunophenotyping ⁴				Х												Х
Soluble protein (immunology) 4				Х				Х				Х				Х
PAXGene RNA for expression analysis in whole blood ⁴					Х											
Archived Samples [serum; plasma]	Х		Х		Χ		Χ		Х		Х		Х		Х	

- 1. In selected countries/sites, participants will have the option to use a centralised home nursing provider. Only selected visits will have the option to be performed as a home visit, these will include drug administration, blood draws, participant assessments and data collection. The full specifications of the home nursing services will be outlined in the SRM
- 2. Hematology- platelet count to be analyzed at local laboratory prior to dose; hematology samples to be collected for central laboratory assessments in parallel
- 3. In addition to the pre-dose sample Intensive PK collection may be collected for China, Japan, and country(ies) with participants of non-Asian heritage (TBD) See Table 8 for details of intensive PK sample collection
 - Intensive PK (GSK3228836 and nucleos[t]ide) will be collected at one visit between Week 14 (inclusive) and Week 24 (inclusive) chosen between the site and participant: post dose at 0.5 hr, 1 hr, 1.5 hr, 2 hr, 3 hr, 4 hr, 5 hr, 6 hr, 8 hr, 12 hr, 24 hr, 72 hr, and 168 hr [the site should make all attempts to align the 168 hr post-dose PK with the next scheduled visit's pre-dose PK, see Table 8 for more details]
- 4. For China, collection of these labs will be contingent on agreements with China regulatory (HGRAC), and will be optional for Chinese participants

Table 17 Off-Treatment Follow-Up

Assessments ¹	OT-Day 1	OT-Day 8	OT-Day 22	OT-Day 50	OT-Day 78	OT-Day 106	OT-Day 134	OT-Day 162	Early Termination
Window	± 3	days			± 10	days			
	OT- W1	OT-W2	OT-W4	OT-W8	OT-W12	OT-W16	OT-W20	OT-W24	
Safety Assessments									
AE/SAE review	Х	Х	Х	Х	Х	Х	Х	Х	Х
Concomitant medication review	Х	Х	Х	Х	Х	Х	Х	Х	Х
Symptom directed exam	Х	Х		Х	Х	Х	Х	Х	Х
Vital signs	Х	Х	Х	Х	Х	Х	Х	Х	Х
Patient Reported Outcomes Questionnaire: HBQOL, EQ-5D								Х	
Laboratory			•						
Pregnancy test (women of child bearing potential)	X		Х	X	Х	X	Х	X	X

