4.5.3. Additional Safety Assessments

4.5.3.1. Laboratory Data

Only central lab data will be used for summary analyses and figures; local lab data will be included in listings, as appropriate.

Summary statistics for changes from baseline for each numeric parameter at each visit will be presented, separately for all clinical chemistry parameters, all hematology parameters and all urinalysis parameters.

For immunology parameters, summary statistics for actual value and change from baseline data for each parameter at each visit will be presented, separately for all numeric parameters. Listings will also be created.

Ang-II will be included in the immunology summaries and listings and additionally a listing of all Ang-II lab values will be presented. Plots showing mean actual and change from baseline values of Ang-II over time will be presented.

For categorical immunology parameters c-ANCA and p-ANCA, summary table of baseline Negative to post-baseline Positive, baseline value no change, and baseline Positive to post-baseline Negative will be created. Listing will be created as well.

For coagulation parameters Prothrombin Intl. Normalized Ratio (INR), Prothrombin Time (PT) and Activated Partial Thromboplastin Time (aPTT), summary statistics for actual at each visit will be presented. Listing will be created as well.

Shift tables for laboratory parameters showing baseline toxicity versus maximum post-baseline (on-treatment and off-treatment periods combined) toxicity for each grade (Grade1, Grade 2, etc.) for chemistry and hematology parameters will be provided.

Increase to Grade 3 or higher lab abnormalities for platelets, ALT, AST, INR, total bilirubin, serum creatinine, eGFR, ACR will be summarized.

Laboratory values outside of normal range will be summarized and listed.

Grading categories for laboratory tests are determined using the DAIDS grading system Version 2.1 [National Institute of Allergy and Infectious Diseases. Division of AIDS, July 2017].

Summary of post-baseline hepatobiliary laboratory abnormalities will be provided.

Liver monitoring and stopping event reporting will be summarized and listed. The Liver monitoring and stopping criteria are described in the protocol Section 7.1.1.

The worst-case urinalysis results post-baseline (on-treatment and off-treatment periods combined) relative to baseline will be summarized.

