6.2.2.1. Definitions of Assessment Windows for Early Termination Visits

Laboratory and vital signs data collected at Early Termination Visits will be assigned to assessment windows, according to the actual date.

Analysis	Parameter	Target	Analysi	s Window	Analysis
Set / Domain	(if applicable)		Beginning Timepoint	Ending Timepoint	Timepoint
Lab, Vital	Numeric				
Signs	parameters	1	1	2	Week 1 Day 1
		4	3	6	Week 1 Day 4
		8	7	9	Week 2 Day 8
		11	10	12	Week 2 Day 11
		15	13	18	Week 3
		22	19	25	Week 4
		1+7(x-1)	1+7(x-1)-3	1+7(x-1)+3	Week x
		169	166	172	OT-Week 1
		176	173	179	OT-Week 2
		190	180	203	OT-Week 4
		218	204	231	OT-Week 8
		246	232	259	OT-Week 12
		274	260	287	OT-Week 16

302	288	315	OT-Week 20
330	316	340	OT-Week 24

Notes:

- 1. Week x includes on-treatment weeks 5-24
- 2. Visit windows are to be used for windowing of Early Termination visits only

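### The China schedule departs from the global schedule in two places that Protocol 10.7.1 does not allow for: weekly instead of 4-weekly PT/INR/aPTT in Weeks 9 to 24, and no patient-reported outcomes at Early Termination

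*Protocol*

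**What the plan says.** Protocol 10.7.1 makes the collection of exploratory and biomarker laboratory tests in China depend on agreement with the national regulator, and then says "otherwise the SoA should be the same as the main study protocol". PT/INR/aPTT is listed with the protocol-required safety tests in Appendix 2 (Table 13). Its row in the China tables does not carry the footnote that marks regulator-dependent tests.

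INR enters the liver rules conditionally. One of the permanent-discontinuation conditions in Protocol 7.1.1, Table 6, is ALT at least 3x ULN with "INR >1.5 (if available". Appendix 2 makes the possible Hy's Law report depend on "international normalized ratio (INR) >1.5, if INR measured". The notes to Table 6 say that clinically significant deterioration in liver parameters "must be confirmed by retesting ALT, total bilirubin, direct bilirubin, and INR (if available".

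For INR, PT and aPTT, SAP 4.5.3.1 says that "summary statistics for actual at each visit will be presented". It also plans a summary of "Increase to Grade 3 or higher lab abnormalities for platelets, ALT, AST, INR" and other parameters. Neither is restricted to visits that both schedules share.

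For patient-reported outcomes, the off-treatment table for China has the row "Patient Reported Outcomes Questionnaire: HBQOL, EQ-5D" marked at Off-Treatment Week 24 only. Global Table 4 marks Off-Treatment Week 24 and Early Termination.

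**The concern.** The schedule tables determine what a site collects. A general statement that two schedules agree does not help a site whose own table shows something else.

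Two consequences follow for coagulation. First, a by-visit summary for a week sampled in one country describes that country, although the table would be labelled by treatment arm for the whole population. Second, Table 6 counts INR only where a value exists. For a participant with ALT from 3x to below 10x ULN, bilirubin at or below 1.5x ULN and no hepatitis symptoms, INR is the one laboratory value that separates no Table 6 row from permanent discontinuation. If routine INR is drawn four times as often in one region, the chance that such a value exists differs by region.

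For the PROs, what is at stake is smaller: an exploratory endpoint with no scheduled post-baseline value for some participants in one country.

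**Working it through.** No stated figure has to be reproduced. The check is a count of marks in the PT/INR/aPTT rows.

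| Period | Global | China | China only |
|---|---|---|---|
| Day 1 to Day 50 (Tables 2, 15) | 2 (Days 1, 29) | 2 (Days 1, 29) | 0 |
| Weeks 9 to 24 (Tables 3, 16) | 4 (Weeks 9, 13, 17, 21) | 16 | 12 |
| Off-treatment (Tables 4, 17) | 6 (OT-Weeks 1, 4, 12, 16, 20, 24) | 6 (same) | 0 |
| Day 1 to OT-Week 24 | 12 | 24 | 12 |

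The China-only visits are Weeks 10-12, 14-16, 18-20 and 22-24. In Table 16 the pregnancy, anti-HBsAg and anti-HBeAg rows keep their 4-weekly pattern, so the full row of coagulation marks does not look like a text-extraction fault.

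Share of visits with scheduled coagulation that are China only:

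- Weeks 9 to 24: 12/16 = 75%
- on treatment, Day 1 to Week 24: 12/(2 + 16) = 12/18 = 67%
- post-baseline: 12/23 = 52%
- Day 1 to OT-Week 24: 12/24 = 50%
- with screening added: 12/25 = 48%

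Each China participant who completes the period has 16 - 4 = 12 extra scheduled samples.

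**Which other values could enter those 12 summaries.** SAP 6.2.2 keeps unscheduled visits out of by-visit tables, so event-triggered INR retests elsewhere would not fill the gap. SAP 6.2.2.1, however, states: "Laboratory and vital signs data collected at Early Termination Visits will be assigned to assessment windows, according to the actual date". Global Table 4 includes coagulation at Early Termination, so a few values from other countries can fall in those weeks. The accurate description is therefore almost entirely China, not only China.

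**Routine detection of a raised INR (illustration; the duration of a rise is my assumption, not a figure from the documents).** Global coagulation visits stay four weeks apart up to OT-Week 1, which is planned for Day 169, one week after the Week 24 visit. Suppose a rise begins at a random weekly visit from Week 9 to Week 24 and spans k consecutive weekly visits. The global schedule samples it for 4, 8, 12 and 16 of the 16 starting visits when k = 1, 2, 3 and 4, that is 25%, 50%, 75% and 100%. The China schedule samples it in every case. The gap runs from 75 percentage points for a one-visit rise to none for a rise spanning four visits. This covers scheduled sampling only and ignores retests triggered by ALT.

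**PROs.** Scheduled HBQOL/EQ-5D visits are Day 1, OT-Week 24 and Early Termination in the global tables, and Day 1 and OT-Week 24 in the China tables. A China participant who leaves the study before OT-Week 24 has 0 scheduled post-baseline assessments; a participant elsewhere has 1.

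**The case against.** The best defence is that little depends on this. No Table 6 row is met by INR alone, since each requires raised ALT. Chemistry, including ALT and bilirubin, is scheduled at every visit of Weeks 9 to 24 in both schedules. Table 6 asks for an INR retest on clinically significant deterioration in all regions, with results evaluated before the next dose, and sites may add tests at any time. The coagulation outputs are descriptive, the default continuous summaries show n, SAP 4.6.2 repeats key safety analyses for mainland China, and the primary endpoint uses HBsAg and HBV DNA only. The PROs are exploratory, and a China participant who stops treatment but stays in follow-up is still assessed at OT-Week 24.

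Most of this stands, and it is why the point is minor. It does not remove the contradiction. The retest is itself conditional on INR being available, and the mandatory follow-up list in 7.1.1 does not name INR, so a regional difference is reduced but not excluded.

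Three stronger readings are tempting and are not supported:

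- **A reader might infer that most by-visit coagulation summaries contain only China data.** That proportion holds on treatment, but over Day 1 to OT-Week 24 it is half, and Early Termination values from elsewhere can enter.
- **A reader might infer that sampling frequency alone decides a participant's Table 6 row.** Weekly ALT and the retest rule contradict this. In the earlier study described in Protocol 4.2.1, 33% of treatment-naive participants had ALT of at least 3x ULN, but without associated changes such as in bilirubin or INR. ALT rises of this size may be common; the documents give no rate for isolated INR above 1.5.
- **A reader might infer bias between arms.** Participants are centrally randomised and each country's schedule is the same in every arm, so a regional sampling difference is not a difference between arms.

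**Conclusion.** Wrong as written, as an internal inconsistency of minor severity. Protocol 10.7.1 conflicts with Table 16 for PT/INR/aPTT (16 visits against 4) and with Table 17 for the Early Termination PRO, and its exception covers neither.

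The part whose size is known is the schedule: 12 of the 16 visits in Weeks 9 to 24 have scheduled coagulation data from China only, or 12 of 24 from Day 1 to OT-Week 24. The by-visit summaries for those 12 visits would rest almost entirely on China participants. This assumes that sites follow their own table.

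The effect on detecting INR above 1.5 has a clear direction but no computable size, because the documents give neither the number of China participants nor the frequency or duration of INR rises. The number of China participants leaving early without a post-baseline PRO is likewise unknown.

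Nothing here settles which coagulation frequency is right. The statement in 10.7.1 that the schedules agree shows that no difference was declared; it does not show which table carries the mistake.

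**What to change.** Reconcile Protocol 10.7.1, Table 16 and Table 3 for PT/INR/aPTT, and Table 17 with Table 4 for HBQOL/EQ-5D at Early Termination. The choice of frequency belongs to the sponsor's clinical and safety staff. If, for example, the China row were matched to the global one, both regions would have 12 coagulation visits from Day 1 to OT-Week 24; whichever row is changed, the China-only count falls from 12 to 0.

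If a difference is intended, say so in 10.7.1 with the reason. Then add a sentence to SAP 4.5.3.1 that either limits the by-visit coagulation summary to visits scheduled in all countries or presents China separately.

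The cost is a correction to two table rows, or a sentence in 10.7.1, at the next amendment, and at most one SAP sentence. Where samples have already been taken under the differing schedules, the SAP sentence is worth adding in any case, because a later correction does not change what was collected.
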